#### 4.12 Research instrument

For collection of primary data about patient a semi-structured questionnaire will be developed based on research objective. Pre-testing of the questionnaire will be done on other patients admitted at the same facility. After the pretesting, amendment of the items and question will be done based on study finding. In the final questionnaire both structured and open questions will be kept.

A check list will be prepared to compile the data from hospital records, treatment records, outcome of treatment and laboratory investigation reports.

#### 4.13 Data collection procedure:

Current study involves collection of both primary and secondary data. Primary data will be collected by face to face interview of the patients or patient's attendant by the researcher at health facility during the period of hospital stay, upon their consent and convenience. Socio demographic and personal information will be recorded from patient through interview, with a semi structured pre-tested questionnaire. Information regarding risk factors and risk behavior will be inquired taking effort to minimize the recall bias.

Secondary data about present state and diagnosis will be collected from hospital record as well as from treatment sheet. For acquiring secondary data a structured checklist will be used.

#### 4.14 Data processing

Data processing will include data cleaning and quality control check, editing of data, coding of data and data entry into computer. The edited data will then be entered on to the template of SPSS® 16 and STATA® 10/IC.

#### 4.15 Data analysis

The edited data will then be entered on to the template of SPSS® 16 and STATA® 10/IC.

For Back ground variables and socio-demographic data descriptive statistics and relative frequency (percentage) will be generated.

Through univariate analysis the base line characteristics and treatment outcome will be compared. The effect of treatment will be identified through Multivariate analysis after adjusting for possible confounders. Relative risk with 95% CI will be generated through binary logistic regression adjusting for all possible confounders.

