4.1 Study design

Study Type: Interventional.

Primary Purpose: Treatment

Study Phase: Phase 1/Phase 2

Interventional Study Model: Parallel Assignment

Participants will be placed in either of the 2 groups, depending on

the number of harvested total stem cell count.

Those having a harvested total "Adipose Derived Stem Cell

(ADSC)" count (in 5 ml SVF solution) between 1 x 10^6 to 2 x

10^6 will be placed in "Group A".

13

Those having a harvested total "Adipose Derived Stem Cell (ADSC)" count (in 5 ml SVF solution) more than 2 x 10^6 will be placed in "Group B".

Both groups will be studied for Phase I/ Phase II trial by the proposed outcome measures over the stipulated time frame.

Those having a harvested total "Adipose Derived Stem Cell (ADSC)" count (in 5 ml SVF solution) less than 1 x 10^6 will be excluded from the study.

Number of Arms: 2

Masking: Triple (Participant, Care Provider, Outcomes Assessor)

Allocation: Non-Randomized

Enrollment: 31 [Anticipated]

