#### 4.2 Arms and Interventions

Arms: Participants having a harvested total "Adipose Derived Stem Cell (ADSC)" count (in 5 ml SVF solution) between 1 x 10^6 to 2 x 10^6 will be placed in "Group A".

Participants having a harvested total "Adipose Derived Stem Cell (ADSC)" count (in 5 ml SVF solution) more than  $2 \times 10^6$  will be placed in "Group B".

Interventions: Both group A and Group B will be injected intravenously with harvested 5 ml of SVF containing Autologous Non Expanded ADSC and outcome will be observed over the period of 1(one) year.

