#### 4.8 Eligibility criteria

#### 4.8.1 Inclusion criteria

A patient is eligible for the study if all of the followings apply:

- a) Aged 18-80 years (inclusive)
- b) With chronic kidney disease (CKD)stage 3 to 5 (eGFR 60 to 0 mL/min/1.73m2 (inclusive)) Note: eGFR = estimated glomerular filtration rate
- c) Having provided informed written consent.

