#### 4.8.2 Exclusion criteria

Any patient meeting any of the exclusion criteria will be excluded from study participation.

- 1) Known hypersensitivity to any component used in the study.
- 2) With inadequate hematologic function with: absolute neutrophil count (ANC) <1,500/μL OR platelets < 100,000/μL OR Hemoglobin < 8 g/dL
- 3) With impaired hepatic function with: serum bilirubin, aspartate aminotransferase (AST), alanine aminotransferase (ALT) or alkaline phosphatase (AKP), prothrombin time above and normal reference and serum albumin below normal reference range.
- 4) With hemoglobin A1c (HbA1c) > 8.0%
- 5) With serious prior or ongoing medical conditions (e.g. concomitant illness such as cardiovascular (e.g. New York Heart Association grade III or IV), hepatic e.g. Child-Pugh Class C), psychiatric condition, alcoholism, drug abuse), medical history, physical findings, ECG findings, or laboratory abnormality that in the investigators' opinion could interfere with the results of the trial or adversely effect the safety of the patient

- 6) Pregnant or lactating women or premenopausal with childbearing potential but not taking reliable contraceptive method(s) during the study period
- 7) With known history of human immunodeficiency virus (HIV) infection or any type of hepatitis
- 8) Judged to be not applicable to this study by investigator such as difficulty of followup observation
- 9) With any other serious diseases/medical history considered by the investigator not in the condition to enter the trial
- 10) Known or suspected abuse of alcohol or narcotics
- 11) With known history of cancer within past 5 years
- 12) With any autoimmune disease
- 13) With congenital kidney disease
- 14) With precancerous condition or with raised tumour markers like Alpha feto protein, Carcino embryonic antigen (CEA), C.A 19.9, C.A 125, Serum PSA above normal reference range.
- 15) Participants having a harvested total "Adipose Derived Stem Cell (ADSC)" count (in 5 ml SVF solution) less than 1 x 10^6 will be excluded from the study.

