#### 4.9 Treatment allocation

All subjects would be submitted for Stromal Vascular Fraction (Autologous Adipose Derived Mesenchymal Stem Cell) Based Treatment for Chronic Kidney Disease

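### Section 4.15 promises an adjusted treatment effect, but every patient receives SVF and no comparator is described, so no regression coefficient can estimate SVF versus no SVF

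*Combined protocol and SAP*

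**What the plan says.** Two sentences in section 4.15 carry the whole inferential plan. The first is "The effect of treatment will be identified through Multivariate analysis after adjusting for possible confounders". The second is "Relative risk with 95% CI will be generated through binary logistic regression adjusting for all possible confounders". Neither names an outcome, an exposure, a comparison or a list of covariates.

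The design they apply to is set out elsewhere:

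- Section 4.9: "All subjects would be submitted for Stromal Vascular Fraction".
- Section 4.2: "Both group A and Group B will be injected intravenously with harvested 5 ml of SVF".
- Section 4.1: patients are grouped by "the number of harvested total stem cell count", with Group A at 1 to 2 million cells and Group B above 2 million. The section states "Allocation: Non-Randomized".
- Sections 4.1 and 4.8.2 (criterion 15): patients with a count below 1 million "will be excluded from the study".
- Section 4.11.1: Phase II outcomes (b), (c) and (d) are changes from baseline to week 24.
- Section 3.2: objective (ii) concerns the role of SVF across CKD stages, and objective (iii) concerns reversing or limiting progression.

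**The concern.** To identify a treatment effect by regression, some patients must have the treatment and others not, or an outside reference must stand in for the untreated. The plan has neither. Adjusting for confounders addresses imbalance between exposed and unexposed patients, and here there are no unexposed patients. This is a problem of identification, so neither a larger sample nor better covariates would cure it.

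What is at stake is how the results will be read. As section 4.15 stands, the report could present an adjusted coefficient as the effect of SVF when it reflects natural course, changes in other medicines, or the kind of patient who yields more cells. Objective (iii) is the most exposed. Limiting progression is a statement about what would have happened without SVF, and a stable eGFR in treated patients cannot supply that.

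**Working it through.** **1. What the design can estimate.**

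| Contrast | Available? | What it measures |
|---|---|---|
| SVF versus no SVF | No: all treated (4.9), no comparator described | – |
| Before versus after, same patients | Yes (4.11.1) | Any SVF effect plus natural course, possible regression to the mean and changes in other medicines |
| Group A versus Group B | Yes (4.1, 4.2) | Cell-count contrast among treated patients, confounded by whatever determines yield |
| By CKD stage | Yes (objective ii; stage recorded in Questionnaire 1) | Difference in change between stages among treated patients |

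Sections 4.11.2 (k) and (l) record changes in antihypertensive and hypoglycaemic medicines at each visit, so the plan itself allows for co-treatment to change.

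**2. The plan's own sample size.** Inputs from section 4.6: two-tailed alpha 0.05, beta 0.20, E = 0.5, S = 1.0, A = 1.000.

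N = A × (1.960 + 0.842)² / (E/S)² = 7.849 / 0.250 = 31.4, given as 31. The figure reproduces. It is a one-sample formula, so the study is sized for a single mean change in all patients, not for a comparison of two groups.

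**3. A versus B with 31 patients.** Two-sample t test, two-sided 0.05, noncentrality = 0.5 / √(1/nA + 1/nB). The plan fixes no split, so the splits are assumptions.

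| Split | Power at 0.5 SD | Difference with 80% power |
|---|---|---|
| 15/16 | 27% | 1.04 SD |
| 10/21 | 24% | 1.11 SD |
| 8/23 | 22% | 1.19 SD |

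By the normal approximation, two equal groups at the same E and S need 2 × 7.849 / 0.250 = 62.8, so 63 per group and 126 in total.

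**4. Before/after change when SVF does nothing (illustration).** One-sample t test, two-sided 0.05, 30 degrees of freedom, noncentrality = drift × √31. The drift values are assumed because the documents give none. Section 4.15 names no test; this one is inferred from section 4.6.

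| Drift from other causes | Noncentrality | Chance of a significant change |
|---|---|---|
| 0 SD | 0 | 5% |
| 0.2 SD | 1.11 | 19% |
| 0.3 SD | 1.67 | 37% |
| 0.5 SD | 2.78 | 77% |

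The direction of drift is unknown: improvement would read as benefit, decline as harm.

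**5. The relative-risk sentence.** Binary logistic regression estimates an odds ratio. With illustrative risks of 0.3 and 0.6 the relative risk is 0.6/0.3 = 2.0, while the odds ratio is (0.6/0.4)/(0.3/0.7) = 3.5. With 0.1 and 0.2 they are 2.0 and (0.2/0.8)/(0.1/0.9) = 2.25.

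On adjustment, a binary outcome in 31 patients has at most 15 in its rarer category. Questionnaire 1 alone offers age, sex, four CKD stages (three indicator terms) and seven named comorbidities: 1 + 1 + 3 + 7 = 12 terms before any medicine is counted. That is at best 15/12 = 1.25 patients in the rarer category per term. Adjusting for every possible confounder is not feasible.

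**The case against.** The strongest reply is that the plan is already an early-phase, openly non-randomized study. Its Phase II outcomes are defined as change from baseline and its sample size is one-sample, so the first sentence of section 4.15 may be loose wording rather than a real claim. A single-arm Phase 1/2 study is legitimate, and much of the remedy restates existing endpoints. That bears on cost more than on substance: section 4.15 is the only analysis text, and it says the effect will be identified.

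Several stronger readings are tempting, and the documents do not support them.

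- **That A versus B is the only between-group contrast.** It is not. CKD stage is recorded at every visit and objective (ii) asks about it.
- **That A versus B says nothing about SVF dose.** The infused volume is the same, but the cell count differs by definition. The contrast is an observational cell-dose association. Adjustment can be attempted under the usual assumptions, but the result is still not SVF versus none.
- **That the relative-risk sentence also claims a treatment effect.** It does not say so and could concern stage or prognostic factors. Its demonstrable faults are the unnamed outcome and exposure, the odds ratio, and the unlimited adjustment.
- **That regression to the mean is large.** Criterion (b) reads "With chronic kidney disease (CKD)stage 3 to 5 (eGFR 60 to 0 mL/min/1.73m2 (inclusive", so selection by the threshold affects mainly patients near the upper limit. No rule for the qualifying measurement and no baseline distribution is given. It is possible, but its size cannot be judged.
- **That 77% is the trial's false-positive rate.** It is the power of a one-sample test at an assumed 0.5 SD shift. It shows only that such a test cannot tell one cause of change from another.

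**Conclusion.** The first sentence of section 4.15 is wrong as written. With SVF given to all and no comparator described, no adjusted coefficient can estimate SVF versus no SVF. This follows from sections 4.1, 4.2, 4.9 and 4.15 alone and rests on no numerical assumption.

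The figures show scale only. Power for A versus B depends on the assumed splits and on carrying over the plan's 0.5 SD; the before/after percentages depend on the assumed drifts and the inferred test. The second sentence needs repair for the separate reasons in step 5 of the working. Nothing here challenges the single-arm design, the within-patient endpoints or the incidence of adverse events in outcome (a).

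**What to change.** Replace both sentences in section 4.15 so that:

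1. Outcomes (b) and (c) are reported as within-patient change from baseline with 95% CI. Outcome (d) is reported as change in the ordinal dialysis score, with proportions improved, unchanged and worse and their CIs. All three are labelled uncontrolled and not attributable to SVF.
2. Comparisons by group (or harvested count) and by CKD stage are reported as exploratory associations among treated patients, adjusted at most for a small prespecified set such as baseline eGFR, and not as a treatment effect.
3. Any binary analysis names its outcome and exposure, uses few covariates, and either reports an odds ratio or uses a method that estimates a relative risk directly.
4. Conclusions on objectives (ii) and (iii) are worded as observed change, with a statement that limiting progression cannot be established without a comparator.

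The cost is rewording and a more modest efficacy claim. Patients, visits, tests, groups and sample size stay as they are.

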#### 4.6 Sample size determination:

 $\alpha$  (two-tailed) = Threshold probability for rejecting the null hypothesis. Type I error rate.

 $\beta$  = Probability of failing to reject the null hypothesis under the alternative hypothesis. Type II error rate.

E = Effect size

 $S(\Delta)$  = Standard Deviation of the change in the outcome.

Here,  $\alpha = 0.05$ 

 $\beta = 0.20$ 

E = 0.5

 $S(\Delta) = 1.0$ 

The standard normal deviate for  $\alpha = Z_{\alpha} = 1.960$ 

The standard normal deviate for  $\beta = Z_{\beta} = 0.842$ 

A = 1.000

$$B = (Z_{\alpha} + Z_{\beta})^2 = 7.849$$

$$C = (E/S(\Delta))^2 = 0.250$$

Sample size N = AB/C = 31 (approx.)

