#### 4.11 Outcome measures

#### **4.11.1 Primary Outcome Measure**

a) Incidence of minor adverse events (MAEs), serious adverse events (SAEs) which may be immediate, early or late - for Phase I [Time Frame: Week 48]

Minor adverse events (MAEs):

i) Pain from lipo-suction > 7 days (Early)

- ii) Fever > 7 days (Early)
- iii) Subcutaneous hematoma / abscess formation (Early)
- iv) Allergic reaction (Immediate)

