#### Serious adverse events (SAEs)

- i) Anaphylaxis (Immediate)
- ii) Pulmonary embolism or infarction (Immediate)
- iii) Outset of any neoplastic change (Late)
- iv) Outset of new Cardiovascular events (Late)
- v) Outset of new Cerebrovascular or neurological events (Late)
- vi) Reactivation of treated tuberculosis (Late)
- b) Change from baseline to 24 week visit in estimated glomerular filtration rate (eGFR) and split renal function in all patients for Phase II [Time Frame: Weeks 0, 24]
  - eGFR with split renal function will be evaluated using DTPA Renogram.
- c) Change from baseline to 24 week visit in estimated glomerular filtration rate (eGFR) with serum creatinine level in patients with CKD 4 and below for Phase II [Time Frame: Weeks 0, 2, 4, 12, 24]
  - eGFR will be calculated by Serum Creatinine level using MRDR formula during all visits.
- d) Change from baseline to 24 week visit in need for dialysis in patients with CKD 5 for phase II [Time Frame: Weeks 0, 2, 4, 12, 24]

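### Section 4.15 promises a relative risk from a binary logistic regression, which yields an odds ratio, and sets no limit on covariates that 31 patients could support

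*Combined protocol and SAP*

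**What the plan says.** Section 4.15 contains three inferential sentences.

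- A comparison step: "Through univariate analysis the base line characteristics and treatment outcome will be compared".
- An adjusted step with no model named: "The effect of treatment will be identified through Multivariate analysis after adjusting for possible confounders".
- The only named model: "Relative risk with 95% CI will be generated through binary logistic regression adjusting for all possible confounders".

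The binary outcome, the contrast, the confounders, their number and any selection rule are all left unstated. Section 4.16 adds cross tables with test statistics in footnotes, and no model.

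Section 4.1 gives an enrollment of 31 in two non-randomized groups, A and B, set by harvested cell count. Under section 4.9 every patient receives SVF, so A v B is the only between-group contrast.

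The primary outcomes in section 4.11.1 are:

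- (a) "Incidence of minor adverse events (MAEs), serious adverse events (SAEs) which may be immediate, early or late";
- (b) "Change from baseline to 24 week visit in estimated glomerular filtration rate (eGFR) and split renal function in all patients for Phase II";
- (c) creatinine-based eGFR change, "with serum creatinine level in patients with CKD 4 and below for Phase II";
- (d) "Change from baseline to 24 week visit in need for dialysis in patients with CKD 5 for phase II", scored 0 to 7.

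No binary cut-off is defined for (b) to (d). The sample size in section 4.6 rests on the "Standard Deviation of the change in the outcome".

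**The concern.** There are two faults in one sentence.

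**Label.** The exponentiated coefficient of a logistic model is an odds ratio. Reported as a relative risk, it overstates the effect whenever the outcome is common. A relative risk can be had by standardizing predicted risks from the fit, or from a log-binomial or modified Poisson model, but the plan mentions none of these.

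**Covariates.** Group membership follows cell yield rather than randomization, so adjustment would carry real weight in any A v B comparison. Yet the plan neither names nor caps the covariates. Questionnaire 1 in Annexure C records age, sex and nine numbered diagnosis entries (CKD itself and an open category among them), so a list of about eight is easy to reach, although not all of these are confounders. With 31 patients such a model may have no finite estimate, or may converge to an extreme one by chance.

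**Working it through.** **The plan's own figure.** Section 4.6 gives N = (1.960 + 0.842)² / (0.5/1.0)² = 7.849 / 0.250 = 31.4, stated as about 31. It reproduces, and it is not disputed here. The formula is for one mean change and makes no allowance for covariates.

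**Odds ratio against relative risk.** OR = [p1/(1−p1)] / [p0/(1−p0)]. The risks are assumed, because the documents give none.

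| p0 | p1 | RR | OR |
|---|---|---|---|
| 5% | 7.5% | 1.50 | 1.54 |
| 10% | 15% | 1.50 | 1.59 |
| 20% | 30% | 1.50 | 1.71 |
| 30% | 50% | 1.67 | 2.33 |
| 30% | 60% | 2.00 | 3.50 |

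In whole patients, 4/16 v 8/15 gives RR = 0.533/0.250 = 2.13 and OR = (8/7)/(4/12) = 3.43. The unadjusted 95% CI for the OR is 0.75 to 15.67.

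**Room for covariates.** Of 31 patients, at most 15 are in the smaller outcome class. As a rule of thumb, 10 per model term allows one term (the group itself) and 5 per term allows three.

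**No covariates.** An ordinary logistic fit has no finite group estimate if either group has zero events. With assumed groups of 15 and 16:

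P = 1 − [1 − (1−p)^15] × [1 − (1−p)^16]

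- p = 0.20: 1 − (0.965 × 0.972) = 0.062
- p = 0.10: 1 − (0.794 × 0.815) = 0.353

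**With covariates.** Simulation settings: groups of 15/16, no true group effect, one prognostic covariate (log OR 0.7 per SD), about half the covariates continuous and half binary at 50%, and 1,500 to 3,000 datasets per setting. No usable estimate means non-convergence or a standard error above 50.

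| Covariates | No usable estimate at 40/20/10% events | OR above 3 or below 1/3 among usable fits, at 40/20% events |
|---|---|---|
| 0 | about 0.1/6/35% | about 16/21-24% |
| 1 | 0.1/7/37% | 20/30% |
| 3 | 0-1/8-14/42-52% | 27/37% |
| 8 | 8-11/37-48/79-85% | 46-47/52-56% |

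The ranges for three covariates reflect the mix of covariate types: at 20% events, 8.4% fail with one binary covariate and 12.7% with two. Failures of the group term alone are 0.2/8/40% with three covariates and 8/42/81% with eight, so the trouble is not confined to nuisance terms.

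**Sensitivity.** An 8/23 split gives 2.0/22.5/59.7% with three covariates and 9.4/49.5/86.3% with eight. Binary covariates at 20% prevalence give 9.7/31.8/66.9% and 36.6/77.0/96.0%.

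Penalized (Firth) fits were finite in all 500 datasets in each setting tried (0, 1 and 8 covariates).

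**The case against.** The best reply has four parts.

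1. *The two harms rarely coincide.* If events are uncommon, as may hold for several of the listed serious events, the label gap is small. Most of the failure with three covariates at 10% events (about 35 of 42-52 points) is then present with no covariates at all. If events are common, a model with up to three covariates usually fits. This stands and limits the severity. It does not rescue the sentence: one fault or the other applies at most event rates, and instability among usable fits persists at 40% events.

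2. *The model is not tied to the efficacy outcomes.* A reader might infer that logistic regression is the planned analysis for GFR change and the dialysis score, since it is the only model named. Section 4.15 does not say so; it leaves the treatment effect to a multivariate analysis of unnamed type. That gap is missing detail and a separate matter. Likewise, adverse events are the natural use of a binary model, but no section makes the link, and 4.11.1 asks only for incidence.

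3. *Covariates picked after seeing the data.* A reader might infer this too. The text supports only that they are not prespecified; read literally, adjusting for everything involves no selection. Nor is the univariate step described as a screen.

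4. *Cross tables in 4.16 give an unadjusted view.* They do, in part, but with no stated interval, and they leave the promised adjusted relative risk as it is.

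**Conclusion.** The point holds in this form: the named model does not produce the named measure, and an uncapped covariate list is not supportable with 31 patients. The mislabelling is material for common outcomes (RR 1.67 shown as 2.33) and minor for rare ones (1.50 shown as 1.54). The covariate problem is severe with about eight covariates, and modest with three when events are common. At 10% events an ordinary logistic fit is unreliable whatever the covariates.

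The odds-ratio arithmetic and the limit of 15 in the smaller class are certain. The failure rates depend on assumed event rates, group sizes and covariate mix, none of which the documents supply. This should be fixed, but it is a fault of analysis wording: it does not undermine the sample size calculation or the design.

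**What to change.** Replace the last sentence of section 4.15 with:

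> For binary outcomes, proportions with exact 95% CIs will be given overall and by group, with an unadjusted risk difference and exact CI. Any regression will contain the group term and at most one covariate named before analysis. It will report a relative risk by modified Poisson, log-binomial or marginal standardization, or else an odds ratio labelled as such. When events are sparse, a penalized or exact method will be used or no adjusted estimate will be given.

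Add that logistic regression will not be used for the change-from-baseline primary outcomes, and that the A v B comparison of GFR change will be adjusted for its baseline value, which Annexure D already collects at week 0. Fuller specification of the primary and secondary outcome models should be handled separately.

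The change needs no extra patients or data. Its costs are:

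- Residual confounding between the cell-yield groups remains and must be stated as a limitation.
- Uncommon events may get no adjusted estimate. Exact intervals are wide: 0/31 gives 0 to 11.2%, and 3/31 gives 2.0 to 25.8%.
- A v B stays imprecise for continuous outcomes. With all 31 patients and before baseline adjustment, the 95% half-width is t(29) × √(1/15 + 1/16) = 0.74 SD, against t(30)/√31 = 0.37 SD for the overall mean change. Creatinine eGFR is restricted to CKD 4 and below. If 16 qualified, split 8/8 (an assumption), the half-widths are t(14) × √(1/8 + 1/8) = 1.07 SD and t(15)/√16 = 0.53 SD.
- The team must confirm that SPSS 16 and STATA 10/IC support the chosen method.
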